## 7 Statistical analysis plan

Primary outcomes

- 1. Venous pH at 1 hour
- 2. Systolic blood pressure at 1 hour
- 3. Glucose at 1 hour
- 4. Beta-hydroxybutyrate level at 1 hour

Participant characteristics will first be summarized using means (standard deviations), medians (interquartile range), and counts (percentages) as appropriate for the type of variable and its distribution. We will plot summary estimates of venous pH, glucose, ketone levels, and systolic blood pressure over time, overall and stratified by SGLT2i use and ketone ester dose. We will compare whether achieved venous pH, glucose, ketone levels, and systolic blood pressure vary by background SGLT2i use, accounting for related baseline measurements. Sensitivity analysis will adjust for age, sex, ketone ester dose, eGFR, and hemoglobin a1c (if available). Repeated measures techniques (accounting for clustering at the level of the participants) may be used to assess overall changes in pH, ketone levels, systolic blood pressure, and glucose. We will describe peak ketone concentrations achieved by arm. Similarly, we will assess the relationship between peak ketone levels (dependent variable) and dose of KE (independent variable). P<0.05 will be used to indicate statistical significance.

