We now have a unique opportunity to study a ketone ester (KE), (R)-3-hydroxybutyl (R)-3-hydroxybutyrate (commercially known as "DeltaG"), that provides systemic ketosis in a deep phenotyping study of HF patients. Initial studies of DeltaG demonstrated significant improvement in exercise capacity among endurance athletes. In this first study, we attempt to find the optimal dose of the ketone product. As patients may be taking minimally ketogenic medications (SGLT2 inhibitors), we will study the pharmacokinetic effects of ketone ester with patients on, and not on, these medications.

Our Specific Aims are as follows:

Aim 1. To assess the pharmacokinetics and safety of ketone ester in patients on, and not on, SGLT2 inhibitors. We will perform serial peripheral blood sampling to understand the effects of acute ketone ester on pH, glucose, systolic blood pressure, and ketone levels to find an optimal dose of the product.

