## 5.3 Pharmacokinetic study:

SGLT2i are standard-of-care ketogenic medications in HFrEF that minimally raise ketone levels though still well within normal limits (0.10mM to 0.13mM, normal <~0.5mM) through reducing insulin:glucagon ratio. Since exogenous ketones *increase* this ratio as shown in our previous work and *reduce* endogenous ketosis, the combination of exogenous ketones and SGLT2i is not expected to perpetuate ketoacidosis risk by SGLT2i (which has not been a significant concern in clinical trials of HFrEF). Further, recent work has supported the safety of ketogenic interventions in patients taking SGLT2 inhibitors. Additionally, pH changes with robust ketosis by KE are noted (1 study showed a pH decrease of 0.10 to an arterial pH of 7.31 after the ketone drink as an expected change). Nevertheless, we will first perform a dose-finding study in 10 HFrEF participants on SGLT2i and 10 not on SGLT2i to assess safety (Table 1). We will measure venous pH, glucose, blood pressure, and BHB every 60 minutes for 4 hours. After a standardized meal containing carbohydrate (to limit endogenous ketosis), we will assess 5 participants in each stratum using 250 mg/kg to initially target BHB levels ~1-2 mmol/L, and then dose escalate to 500 mg/kg for 5 participants which is predicted to achieve BHB levels ~3 mmol/L (safely achieved in HF patients previously with KE without inducing significant side effects including mild acidosis). This is also the dose used in a recent trial in cardiogenic shock without significant safety concerns but with significant efficacy. We will not escalate past 500 mg/kg given increasing risk for gastrointestinal symptoms.9, 37

Table 1. Pharmacokinetic Stud	y Details and Dose Escalation/De-escalation Plan

Strata	Dose	Timepoints assessed	Endpoints assessed
SGLT2i arm and no SGLT2i arm	250 mg/kg KE for 5 participants, then 500 mg/kg for 5 participants	Every 60 minutes for 4 hours	Venous pH, systolic blood pressure, glucose

Food may be provided to participants if they have hypoglycemia (glucose <55 mg/dl) but otherwise we will ask participants to refrain from consuming food after the ketone drink is administered until the 4 hour blood draw.

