Prior to the ketone drink, we will collect blood –twice - in the fasted status (>8 hours of fasting) and then after a light breakfast. We will collect blood 6 times after ketone drink. There will be at most 8 blood draws as below.

Blood draw number	Approximate time of blood draw	Blood draw for endpoint assessment	Blood draw for storage
1	Fasting, prior to ketone drink		х
2	After light meal, prior to ketone drink		x
3	30 minutes after ketone drink		х
4	60 minutes after ketone drink	Х	x

5	90 minutes after ketone drink		х
6	120 minutes after ketone drink	X	x
7	180 minutes after ketone drink	x	x
8	240 minutes after ketone drink	x	x

Timepoints delinated here are approximate. We aim to draw blood as close to the timeline outlined here, but +/- 15 minutes from the timepoint is considered acceptable without deviation. Likewise, lack of blood draws at times not used for endpoint assessment will not be considered a deviation.

We preferentially enroll unique patients in this study (i.e. 20 different patients). However, in the event of difficult enrollment in the "no SGLT2i arm", participants currently taking an SGLT2i may enroll and hold the SGLT2i for at least 4 days (with the permission of their treating physician). This amount of time is similar to what is advised prior to some procedures (i.e. surgery). Therefore, participants could enroll twice in this study (in each arm).

A total of ~100 mL of blood will be obtained at this visit.

Blood samples will be stored (either within the Duke Heart Center or the Duke Molecular Physiology Institute) at -80C for later analysis. We may perform routine blood testing (metabolic panels, blood counts), comprehensive metabolomic/proteomic profiling from this peripheral blood, as well as other biomarkers, in addition to other testing, pending sufficient funding.

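### Ketone ester dose is left out of the main SGLT2i comparison, and no dose difference with an interval is planned for the four 1-hour outcomes

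*Combined protocol and SAP*

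**What the plan says.** The SAP (Section 7) names four primary outcomes, all at 1 hour: venous pH, systolic blood pressure, glucose and BHB. The comparison it plans is by SGLT2i use: "We will compare whether achieved venous pH, glucose, ketone levels, and systolic blood pressure vary by background SGLT2i use, accounting for related baseline measurements".

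Dose appears in three places in Section 7:

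- Summary plots over time are stratified by SGLT2i use and by dose.
- Dose is one of five added covariates in a secondary model: "Sensitivity analysis will adjust for age, sex, ketone ester dose, eGFR, and hemoglobin a1c (if available".
- For peak ketones only, "we will assess the relationship between peak ketone levels (dependent variable) and dose of KE (independent variable".

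Section 7 mentions no confidence interval; its only inferential criterion is P<0.05.

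Elsewhere, dose is central. Aim 1 (Section 2) measures pH, glucose, systolic pressure and ketones "to find an optimal dose of the product". Section 5.3 sets the lower dose, "we will assess 5 participants in each stratum using 250 mg/kg to initially target BHB levels ~1-2 mmol/L", and then 500 mg/kg for a further 5 per stratum, "which is predicted to achieve BHB levels ~3 mmol/L".

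**The concern.** Dose is a factor of the design, and the protocol itself expects it to move BHB. A design factor with a real effect belongs in the main model. If it is left out, its variation goes into the residual, so the SGLT2i interval is too wide and the test rejects less often than its nominal level. A real SGLT2i difference is then more easily missed, and a missed difference may be read as reassurance about giving the ester to patients on SGLT2i.

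The second loss concerns the study's stated purpose. Someone choosing a dose for the next trial would have plots and a peak-ketone regression, but no stated estimate of how 1-hour pH, systolic pressure, glucose or BHB differ between 250 and 500 mg/kg, and no measure of how uncertain that difference is.

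**Working it through.** **Design count.** 2 strata × (5 + 5) = 20, which matches the planned enrolment. The plan gives no SD, effect size or power, so there is no power figure to reproduce.

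**Inputs from the protocol.** Section 5.3 gives about 1–2 mmol/L BHB at 250 mg/kg and about 3 mmol/L at 500 mg/kg. The implied dose gap D is 3 − 2 = 1 to 3 − 1 = 2 mmol/L, midpoint 1.5. Section 5.3 attaches no time to these levels. Sections 4 and 6 put the peak at about 60 minutes, which supports using the gap at 1 hour, although Section 6 also gives a Tmax of about 1–3 hours.

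**Assumptions.** Within-dose SD s of 0.5 to 1.5 mmol/L (not in the documents); a linear model of the 1-hour value; 20 unique participants; baseline unrelated to dose; two-sided 5% tests.

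**Interval width for the SGLT2i difference.**

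- Dose omitted (intercept, baseline, SGLT2i; 17 df): expected residual variance = s² + 20(D/2)²/17.
- Dose included (16 df): residual variance = s².
- Ratio of widths = √[1 + 20(D/2)²/(17s²)] × t(0.975, 17)/t(0.975, 16), with t values 2.110 and 2.120.

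For D = 1.5 and s = 0.75: 20 × 0.5625/17 = 0.662; 0.662/0.5625 = 1.176; √2.176 = 1.475; divided by 1.005 this is 1.47.

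| Dose gap (mmol/L) | s = 0.5 | s = 0.75 | s = 1.0 | s = 1.5 |
|---|---|---|---|---|
| 1 | 1.47 | 1.23 | 1.13 | 1.06 |
| 1.5 | 1.90 | 1.47 | 1.28 | 1.13 |
| 2 | 2.38 | 1.75 | 1.47 | 1.23 |

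Simulation with a randomly varying baseline gives slightly smaller ratios: 1.05 and 2.34 at the two extremes.

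**Test size and power for BHB** (20,000 simulated trials per setting; the true SGLT2i difference is an illustrative 1.33 SD):

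| Setting | Rejection with no SGLT2i effect, dose omitted | Power, dose omitted | Power, dose included |
|---|---|---|---|
| D = 1.5, s = 0.75, difference 1.0 mmol/L | about 0.8% | about 45% | about 77% |
| D = 1, s = 1.5, difference 2.0 mmol/L | about 4% | about 74% | about 77% |

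With dose included, the rejection rate under no effect is about 5%.

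**The planned sensitivity model.** With HbA1c available it has 8 parameters (intercept, baseline, SGLT2i, dose, age, sex, eGFR, HbA1c), leaving 20 − 8 = 12 df. In the first setting its power for the SGLT2i difference is about 63%. Mean interval half-widths for dose omitted, sensitivity model and dose included are 1.05, 0.86 and 0.72 mmol/L. At equal residual SD its interval for the dose difference is about 16% wider (median) than in the three-term model.

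**What a dose contrast could show.** With 10 v 10 and 16 df the half-width is 2.120 × √(2/10) = 0.95 SD. By the noncentral t distribution, 80% power needs a difference of about 1.33 SD. The 77% simulated above for the same difference is slightly lower because the baseline there varies by chance between groups.

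**If balance fails.** With one stratum at 6/4 and the other at 5/5, omitting dose shifts the SGLT2i difference by 0.1 × D, or 0.10 to 0.20 mmol/L. At 7/3 the shift is 0.20 to 0.40 mmol/L.

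**The case against.** The best reply is that dose is already in the plan, in the plots, the sensitivity model and the peak-ketone analysis, and that balance removes bias. All of that is true. The sensitivity model also recovers part of the lost power, to about 63% in the first setting. But it is not the main result, it spends 12 of 20 degrees of freedom on error only after four extra covariates, and its dose coefficient is not named for reporting. Peak ketone is not the 1-hour value and says nothing about pH, systolic pressure or glucose.

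The power example can also be challenged. The only SGLT2i ketone shift in the protocol is 0.10 to 0.13 mM (Section 5.3), a difference of 0.03. At that size neither model would detect anything: simulated rejection is about 0.9% without dose and 5% with it. The 1.0 and 2.0 mmol/L differences are therefore illustrations. The width ratios do not depend on them.

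The model form is a reading of the text. Section 7 does not say that the SGLT2i comparison is a 1-hour regression, and it leaves repeated-measures techniques optional. The degrees of freedom above hold for the simplest reading.

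Finally, the dose contrast has limits: dosing is sequential and not randomised, the groups are small, and an additive model pools over strata, so it does not isolate patients on SGLT2i at the higher dose. These are reasons to report an interval and label it as estimation, not reasons to omit it.

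**Conclusion.** The concern holds. The main SGLT2i comparison omits a design factor that the protocol expects to affect BHB, and no dose difference with an interval is planned for any of the four primary outcomes. The harm to the SGLT2i comparison is lost precision and a conservative test, not bias, provided the 5/5 split is achieved. For BHB the interval is between 6% wider and 2.38 times as wide, depending on the dose gap and the assumed SD. For pH, glucose and systolic pressure the documents give neither a dose gap nor an SD, so the loss cannot be stated and may be nil. The missing dose estimate affects all four outcomes and does not depend on those assumptions. This should be changed, but it does not invalidate the planned comparison.

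**What to change.** In Section 7, make the main model for each 1-hour outcome: outcome = baseline + SGLT2i use + dose. Report the SGLT2i difference and the 500 v 250 mg/kg difference, each with a 95% confidence interval. Keep age, sex, eGFR and HbA1c as the additions in the sensitivity model.

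State that the dose difference is estimation only: assignment is sequential, and with a half-width of about 0.95 SD it cannot show that the doses are equally safe.

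Two details should be settled in the same edit. Blood is drawn before the drink "in the fasted status (>8 hours of fasting) and then after a light breakfast" (Section 5.3), so say which of the two is the baseline. And since "participants could enroll twice in this study (in each arm" (Section 5.3), add a participant term if anyone does.

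The cost is a few SAP sentences and one degree of freedom. If dose has no effect, the SGLT2i interval widens by about 0.5% (2.120/2.110 = 1.005). No new data or visits are needed.

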#### 4 Published Data on Ketone Ester

DeltaG is a ketone ester (KE) that undergoes complete enzymatic hydrolysis to form BHB (and R-1,3butanediol) by carboxylesterases expressed widely, including within the gastrointestinal tract, liver, and blood. R-1,3-butanediol, itself, is further metabolized in the liver by first-pass metabolism and blood to produce BHB by alcohol dehydrogenase and aldehydye dehydrogenase. BHB undergoes further metabolism to acetoacetate and acetone, though only BHB and acetoacetate are taken up by extra hepatic tissues as energy sources.

KE is eliminated through at least first order kinetics and capacity limited elimination. Elimination is accomplished via 3 predominant means, including (1) conversion to acetone and lung exhalation, (2) renal elimination (of BHB and acetoacetate, though this contribution is negligible particularly during exercise), and (3) uptake by tissues using monocarboxylate transporters for conversion to ATP.

Concentrations of the KE compound of roughly 3-5 mmol/L are reached within 60 minutes at doses comparable to what is studied here. The half-life of the compound is 0.8-3.1 hours. The KE compound has a very favorable safety profile with adverse effects limited to dose-dependent, gastrointestinal distress that typically occur only at the highest levels of administration (714 mg/kg).

Request for IND exemption: We believe this study qualifies under the criteria for IND exemption. DeltaG has been granted **GRAS** status through the FDA as a food, and the GRAS documentation will be separately submitted. We believe this study is exempt from the IND requirements because it meets the conditions of FDA guidance (sections VI.D.1 & VI.D.2). Specifically, DeltaG, as used in this study, is not intended for use "in the diagnosis, cure, mitigation, treatment, or prevention of disease". As DeltaG is only received on *one* study date as an acute study, and endpoints assessed here are for safety, we believe the use of DeltaG fulfills these critiera here. Participants will be notified in the ICF specifically that they will not benefit as a result of participating in the study. The intent of the study is to describe the acute effect of DeltaG (a food) on venous pH, glucose, and blood pressure as a safety mechanism. In addition, the results of this study are not intended to affect the marketing or labeling of DeltaG.

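### The first aim is pharmacokinetic, but section 7 prespecifies no AUC, time of peak or elimination measure for BHB, and dose is not in the main SGLT2 inhibitor comparison

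*Combined protocol and SAP*

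**What the plan says.** Section 2 states the first aim: "To assess the pharmacokinetics and safety of ketone ester in patients on, and not on, SGLT2 inhibitors". Section 1 says the results will inform dosing of a later randomised trial.

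Section 7 lists "Beta-hydroxybutyrate level at 1 hour" as a primary outcome. For the peak it says "We will describe peak ketone concentrations achieved by arm" and "we will assess the relationship between peak ketone levels (dependent variable) and dose of KE (independent variable". The same paragraph also plans:

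- plots of ketone levels over time, by SGLT2 inhibitor use and by dose;
- a baseline-adjusted comparison of achieved ketone levels by SGLT2 inhibitor use, with no time point given;
- repeated-measures methods, permitted but not required, for overall change.

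Dose appears among the covariates of the sensitivity analysis. No AUC, time of peak, half-life or clearance is named.

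On kinetics, section 4 says "KE is eliminated through at least first order kinetics and capacity limited elimination". Section 6 gives a Tmax of about 1-3 hours, a peak at around 60 minutes for the doses used here, and a half-life of 0.8-3.1 hours.

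Section 5.3 plans hourly BHB for 4 hours, although its Table 1 leaves BHB out of the endpoints. Of eight draws, those at 60, 120, 180 and 240 minutes are marked for endpoint assessment. The two pre-drink draws and those at 30 and 90 minutes are marked for storage only, and "lack of blood draws at times not used for endpoint assessment will not be considered a deviation". For timing, "15 minutes from the timepoint is considered acceptable without deviation".

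**The concern.** Neither named summary measures total exposure or elimination. A level at 1 hour depends largely on absorption, and a change in clearance shows mainly afterwards. If elimination is partly saturable, as section 4 says, doubling the dose from 250 to 500 mg/kg should raise total exposure more than twofold, and an early level shows that less clearly than an AUC does.

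Two features blur the comparison further. Each SGLT2 inhibitor stratum is half at each dose, so leaving dose out of the main model puts the dose effect into the residual. And because the 30- and 90-minute draws are storage-only and may be missed, the peak could come from four values in one participant and six in another.

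At stake is whether a dose-finding study delivers a prespecified estimate of how exposure depends on dose and on SGLT2 inhibitor use.

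**Working it through.** The plan states no effect size, SD or power, so there is no figure of its own to reproduce. The draw count is consistent: 2 before the drink + 6 after = 8, of which 4 are endpoint draws.

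**1. Linear check.** From section 6: half-life 0.8-3.1 h. Assumed: one compartment, first-order absorption at ka = 1.0-3.0 per hour, equal dose and volume. Up to a scale factor,

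C(t) = ka/(ka − ke) × [exp(−ke·t) − exp(−ka·t)], with ke = ln 2 / half-life.

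Take ka = 1.5 and let clearance fall by one third (half-life 1.6 to 2.4 h, so ke goes from 0.433 to 0.289):

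- C(1 h): 0.598 to 0.651, ratio 1.09.
- AUC 0-4 h (trapezoid, all six post-drink times): 1.707 to 2.081, ratio 1.22.
- C(4 h): ratio 1.58.

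Over ka = 1.0-3.0 the rises are 8-11% at 1 hour, 10-14% for the peak, 21-24% for AUC 0-4 h and 49-69% at 4 hours.

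**2. Capacity-limited check.** Assumed: dC/dt = absorption input − Vmax·C/(Km + C) − 0.15·C, with ka 0.5-2.0 per hour, Km 0.5-2 mmol/L, Vmax 0.7-2.5 mmol/L/h and the input amount varied. Kept: sets with a peak of 1-2 mmol/L at the lower dose (the section 5.3 target) and Tmax 1-3 h, about 90-110 sets depending on grid spacing.

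| Measure | 25% lower clearance | Dose doubled (ratio) |
|---|---|---|
| 1-hour BHB | +5 to 22% (median about 10%) | 2.1-2.7 |
| Peak | +7 to 30% | not needed here |
| AUC 0-4 h | +12 to 53% (median about 23-24%) | 2.2-3.8 |

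On the log scale the AUC shift is 1.8-2.5 times the 1-hour shift. The mean of the four planned hourly values moves by a median of about 28-29%, at least as much as AUC in every set.

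**3. What 10 against 10 can detect.** Two-sided 5% t-test on logs, SD = sqrt(ln(1 + CV²)). The CV is assumed, and taken as equal for both measures. For 80% power the detectable difference is 1.32 SD, a ratio of 1.30 at CV 20% and 1.87 at CV 50%. Power for illustrative true rises of 8% (1-hour) and 20% (AUC), both inside the ranges above:

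| CV | 1-hour, +8% | AUC, +20% |
|---|---|---|
| 20% | 13% | 50% |
| 30% | 9% | 26% |
| 50% | 6% | 13% |

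**4. Dose left out of the model.** With half of each stratum at each dose and proportional exposure, dose alone contributes a log-scale SD of ln(2)/2 = 0.35. With a between-person SD of 0.20 (CV 20%), the total is sqrt(0.35² + 0.20²) = 0.40, about double.

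**5. Sampling grid.** In the linear model, a trapezoid on baseline plus hourly values falls 4-19% below the true AUC 0-4 h; with all six post-drink values it falls 1-4% below. At a half-life of 3.1 h, AUC 0-4 h holds 48-56% of total AUC.

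**The case against.** A reader might infer that the plan analyses ketone kinetics only through the 1-hour and peak levels, so that clearance differences would be largely missed. The documents do not support that. Section 7 also plans stratified time plots, a comparison by SGLT2 inhibitor use not tied to 1 hour, and possible repeated-measures modelling. A group effect on the four hourly values would be about as sensitive to clearance as AUC (step 2). What remains is that the plots are descriptive, the comparison names no time point, and the modelling is optional with no group-by-time term.

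Nor do the documents show that 1 hour is a poor choice. Section 6 puts the peak near 60 minutes at these doses, section 5.3 sets its dose targets as concentrations, and section 4 describes the endpoints as safety endpoints. That supports keeping the 1-hour outcome. It does not supply an exposure measure for a pharmacokinetic aim.

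Finally, it is tempting to say that AUC would rescue the power. At a CV of 30% or more it would usually miss a 20% difference too. A clearance effect of SGLT2 inhibitors is itself a hypothesis: section 5.3 describes only a small endogenous rise, from 0.10 to 0.13 mM. The case for AUC is therefore estimation, not significance.

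**Conclusion.** The point holds in a limited form: exposure and elimination are not prespecified, and the analyses that could capture them are descriptive, undated or optional. AUC 0-4 h responds roughly twice as much as the 1-hour level, on the log scale, to a 25% change in clearance. That ratio was stable over the parameter sets tried (1.8-2.5), but the percentage shifts depend on assumed absorption and elimination constants, and the power figures on an assumed CV. Leaving dose out of the main comparison is a separate loss of precision, and it needs no kinetic model beyond approximate dose-proportionality. This should be changed before analysis; it does not invalidate the 1-hour outcome.

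**What to change.** In section 7, add BHB AUC from 0 to 4 hours (trapezoid on recorded draw times, starting from a pre-drink value), peak and time of peak as secondary exposure measures. Compare log AUC and log peak by SGLT2 inhibitor use, with dose and baseline BHB in the main model, and by dose. Report ratios with 95% confidence intervals; a 500 to 250 mg/kg ratio of 2 means dose-proportional exposure. Keep 1-hour BHB as primary.

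In the section 5.3 draw table, mark the post-meal pre-drink draw and the 30- and 90-minute draws for BHB assay, so that all participants share one sampling grid. The pre-drink draw is essential, because a trapezoid from time 0 needs it and it is currently storage-only. Reconcile Table 1 with the text on whether BHB is an endpoint.

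Cost: SAP and draw-table wording, and about 3 × 20 = 60 extra BHB assays on draws already scheduled. Those three draws become subject to the deviation rule. AUC 0-4 h remains a partial exposure and should be labelled as such.

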## 6 Risks and Safety Assessment

Ketone Ester: This proposal includes a ketone ester which is commercially available and has been granted "Generally Regarded as Safe" (GRAS) status from the FDA. This KE undergoes complete enzymatic hydrolysis to form BHB (and R-1,3-butanediol) by carboxylesterases expressed widely, including the gastrointestinal tract, liver and blood. R-1,3-butanediol, itself, is further metabolized in the liver and blood to produce BHB. The TMax ranges from ~1-3 hours. Elimination is accomplished via conversion to acetone and lung exhalation, renal elimination, and uptake by tissues using for conversion to ATP (including the brain, heart, kidney, and skeletal muscles). We exclude participants both with a history of significant renal impairment (eGFR <25 ml/min/m^2) or hepatic impairment (history of cirrhosis, alcohol abuse). Peak concentrations of KE are reached around 60 minutes at doses anticipated to be administered here. The half-life of BHB from the compound is 0.8-3.1 hours. Adverse effects are infrequent and dose-dependent; gastrointestinal distress occurs at the highest levels of administration (714 mg/kg), consistent with our own experience. No clinically significant changes in vital signs, lipid levels, blood counts, renal function, and urinalysis parameters were observed at doses similar to those studied here. Participants may be on SGLT2i which are minimally ketogenic medications in themselves with minimal risk for ketoacidosis in HF. As outlined in this section, it is not anticipated that the KE will amplify risk of ketoacidosis with SGLT2i given the differing biologies of endogenous versus exogenous ketosis. However, this potential risk will be outlined to participants who enroll in this study. **Dose:** In this proposal, we will perform a pharmacokinetic study to determine optimal dose without significant safety concerns which will be explored in our pharmacokinetic study. Our product is purchased commercially as "DeltaG" (TdeltaS, Orlando, FL). We have administered these doses proposed here to 15 HFpEF patients in an ongoing study without significant adverse events related to the nutraceutical. We will monitor for any adverse events throughout the study visit. The compound half-life is short as indicated above. To aid intolerability, participants are served a light meal. In addition, water (which may be naturally flavored and/or carbonated) is freely permitted.

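### The main SGLT2i comparison leaves out ketone ester dose, a balanced design factor, which widens the BHB interval for no benefit; put dose in the model and report the 95% CI.

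*Combined protocol and SAP*

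**What the plan says.** Section 7 (Statistical analysis plan) names four primary outcomes at 1 hour: venous pH, systolic pressure, glucose and BHB. The main comparison asks whether the achieved values "vary by background SGLT2i use, accounting for related baseline measurements". Dose is not in that model. The next sentence is where it appears: "Sensitivity analysis will adjust for age, sex, ketone ester dose, eGFR, and hemoglobin a1c (if available". Dose is also used in the stratified plots and in a separate analysis of peak ketone level on dose.

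The section closes with "P<0.05 will be used to indicate statistical significance". The documents name no confidence interval, margin or power for the SGLT2i comparison, and give no sample-size rationale.

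Section 5.3 (Pharmacokinetic study) makes dose part of the design. It assigns "5 participants in each stratum using 250 mg/kg to initially target BHB levels ~1-2 mmol/L" and a further five per stratum to 500 mg/kg, "which is predicted to achieve BHB levels ~3 mmol/L". The same section allows, as a fallback if recruitment off SGLT2i is difficult, that one person takes part in both arms. On within-person correlation, Section 7 says only this: "Repeated measures techniques (accounting for clustering at the level of the participants) may be used to assess overall changes".

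**The concern.** The protocol itself predicts that dose will move BHB by 1 to 2 mmol/L, and it splits dose evenly within each SGLT2i stratum. A factor that is both balanced and expected to be strong is the ideal covariate: including it removes known variation and leaves the contrast unchanged. The main model instead treats the designed difference between 250 and 500 mg/kg as random noise.

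At stake is how much 20 participants can say about Aim 1, which concerns pharmacokinetics and safety on and off SGLT2i. The protocol expects no added ketoacidosis risk from the combination, so a non-significant comparison is a likely result. A p-value alone would then not tell the reader which differences remain compatible with the data, and an interval inflated by dose would overstate that uncertainty for BHB.

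**Working it through.** The plan gives no precision or power figure to reproduce, so the check is of what the design delivers.

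**Inputs from the documents.** n = 10 per SGLT2i stratum, five per dose within each stratum; predicted BHB about 1-2 mmol/L at the lower dose and about 3 at the higher, so a dose gap of 1 to 2 (midpoint 1.5); criterion 0.05.

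**Assumptions.** Two-sided test; within-dose BHB SD *s* of 0.5, 0.7, 1.0 or 1.5 mmol/L; no correlation between pre-drink and post-drink BHB, because pre-drink levels are close to zero; predicted BHB levels apply at 1 hour.

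**Step 1. General precision.** Half-width = t(0.975, df) × SD × √(2/10). With 18 df: 2.101 × 0.4472 = 0.94 SD. A difference of about 1.33 SD is needed for 80% power.

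**Step 2. Error variance for BHB when dose is omitted.** Each person lies gap/2 from the stratum mean because of dose, so dose adds 20 × (gap/2)² to the residual sum of squares:

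residual variance = [18*s*² + 20 × (gap/2)²] / 18.

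At gap 1.5 and *s* = 0.7: (18 × 0.49 + 20 × 0.5625)/18 = (8.82 + 11.25)/18 = 1.115, a residual SD of 1.056 against a within-dose SD of 0.7.

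**Step 3. Half-widths.** Without dose (18 df): 2.101 × 1.056 × 0.4472 = 0.99 mmol/L. With dose (17 df): 2.110 × 0.7 × 0.4472 = 0.66 mmol/L. In the same way, at gap 1.5:

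| Assumed within-dose SD | Without dose | With dose | Ratio |
|---|---|---|---|
| 0.5 | 0.88 | 0.47 | 0.54 |
| 0.7 | 0.99 | 0.66 | 0.67 |
| 1.0 | 1.20 | 0.94 | 0.79 |
| 1.5 | 1.59 | 1.42 | 0.89 |

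At SD 0.7, gaps of 1 and 2 give 0.82 and 1.19 without dose, against 0.66 with it. The least favourable corner, gap 1 and SD 1.5, gives 1.49 against 1.42. Including a baseline term in both models (17 and 16 df) changes these figures little; at SD 0.5 and gap 1.5, for example, they become 0.90 and 0.47.

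**Step 4. Behaviour of the test (simulation, gap 1.5).** At SD 0.7 with no true SGLT2i difference, the nominal 5% test rejects about 0.4% of the time without dose and 5.0% with it. At SD 1.0 the figures are about 1.4% and 5.0%. Power at SD 0.7, without and with dose, is 8% and 33% for a true difference of 0.5 mmol/L, and 52% and 85% for 1.0 mmol/L. Neither difference comes from the documents.

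**Step 5. What the dose term costs.** With baseline already in the model, t rises from 2.110 (17 df) to 2.120 (16 df), a ratio of 1.005. Allowing for chance correlation of baseline with dose, the interval is still less than 1% wider if dose has no effect.

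**Step 6. The existing sensitivity model.** Intercept, SGLT2i, baseline, age, sex, dose, eGFR and HbA1c make 8 parameters, leaving 20 − 8 = 12 df. Its half-width is at least 2.179 × 0.4472 = 0.97 SD before any loss from correlated covariates, against 0.95 SD for baseline plus dose (2.120 × 0.4472), both in units of the same residual SD.

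**Step 7. Enrollment in both arms.** Suppose five people enroll twice with within-person correlation 0.5 (both assumed). The variance of the simple mean difference, in SD² units, is 0.2 − 2 × 5 × 0.5/100 = 0.15, so the SE is 0.387 and the half-width 0.81 SD, against 0.94 if independence is assumed. Modelling the pairing, with the correlation taken as known, gives about 0.77 SD.

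**The case against.** The best defence is that nothing here is an error. The closing P<0.05 sentence is a general convention for the section; it does not forbid intervals, and an adjusted comparison yields an estimate and standard error anyway. Dose is not ignored: it is in the plots, the sensitivity model and the peak-ketone analysis. All of this is correct. Even so, none of those places gives an SGLT2i difference adjusted for baseline and dose alone.

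The second defence is that dose is balanced, so its omission cannot distort the contrast, and the test errs on the conservative side. This also stands, but it answers bias and not precision. A reader might infer that the SGLT2i estimate is biased; under the planned 5/5 split it is not, and bias from dose could arise only if the split became unequal.

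A reader might also infer that the plan will treat a non-significant result as evidence of safety. The documents do not say so, and Section 6 provides for safety separately: "We will monitor for any adverse events throughout the study visit".

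Nor should the power figures be read as a promise that dose adjustment makes the comparison well powered. The only SGLT2i ketone figure in the documents is an endogenous shift from 0.10 to 0.13 mM (Section 5.3). A post-drink difference could be larger, but no document supports 1.0 mmol/L, and at 0.5 mmol/L with SD 0.7 power is low under either model.

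Two further limits are fair. The gain is shown for one of four primary outcomes, since no dose-specific effect is given for pH, glucose or systolic pressure. And the predicted BHB levels are not tied to the 1-hour time point; Section 6 puts TMax at about 1 to 3 hours.

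Finally, a reader might infer that enrollment in both arms invalidates the comparison. It is a fallback, ignoring it is conservative, and the real efficiency gain with five such people is from 0.81 to 0.77 SD.

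**Conclusion.** The point holds as a matter of precision and reporting. Leaving dose out of the main SGLT2i model does not bias the contrast under the planned split, but for BHB it inflates the error term, widens the interval and makes the 5% test conservative. At a dose gap of 1.5 mmol/L, adjusting for dose cuts the half-width to between 0.54 and 0.89 of its unadjusted value as the SD goes from 0.5 to 1.5 mmol/L. At a gap of 1.0 and SD 1.5 the gain is only about 5%.

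These sizes rest on assumed SDs and on the protocol's predicted BHB levels holding at 1 hour. Any gain in power depends on an SGLT2i effect that the documents do not give. For the other three outcomes the gain is unknown, though the cost of the term is negligible. Reporting the interval is worthwhile for all four, because at 10 against 10 a p-value alone leaves differences approaching one SD unaddressed. This is an improvement worth making, not a fault that undermines the study.

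**What to change.** Amend Section 7 so that, for each primary outcome, the main model contains SGLT2i use, the baseline value and ketone ester dose, and the SGLT2i difference is reported with its 95% CI and interpreted through the limits instead of through P<0.05 alone. Keep the model with age, sex, eGFR and HbA1c as the sensitivity analysis; it still has a role because SGLT2i use is not randomized.

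As a minor addition, state that if several people enroll in both arms, the between-arm comparison will allow for within-person correlation. With only one or two such people the correlation would be poorly estimated.

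The cost is wording only: no new data, visits or participants. The downsides are one degree of freedom (an interval at most about 1% wider if dose has no effect) and conclusions that are less categorical than a significance statement.
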